9. STUDY PROCEDURES

The schedule of study procedures for each visit are summarized in [Section 23.2](#) and are described below.

9.1. Pre-study Evaluation (Day -31 to 1)

Before screening, subjects will be informed of the nature of the study, and written consent must be obtained prior to participation. After obtaining informed consent, the following procedures will be carried out:

1. Complete medical history
2. Physical examination, including height, body weight and vital statistics
3. Urine pregnancy test for all females of child-bearing potential
4. Review concomitant medications
5. Collection of blood sample for serological tests for qHBV DNA, qHBsAg, qAnti-HBs, HBeAg, anti-HBe, IgM anti-HBc, anti-HIV, anti-HCV and anti-HDV.
6. Collection of a blood sample for laboratory tests including hemoglobin, hematocrit, complete blood count (total and differential), platelet count, prothrombin time (PT), international normalized ratio (INR), random/faasted blood sugar, total cholesterol, high-density lipoprotein, triglycerides, albumin, iron, ferritin, aspartate aminotransferase (AST), ALT, gamma glutamyl transferase (GGT), creatine phosphokinase (CPK), alkaline phosphatase, bilirubin (total/direct), blood urea nitrogen (BUN), creatinine, sodium, potassium, chloride, and alpha-fetoprotein (AFP).
7. Collection of urine sample for routine urinalysis (appearance, glucose, protein and blood).
8. Calculation of creatinine clearance by the Cockcroft-Gault equation using ideal body weight.
9. FibroScan® test.
10. Ultrasonography for hepatocellular carcinoma (HCC) screening.
11. Confirmation that the subject satisfies all inclusion/exclusion criteria.

9.2. Baseline (Day 1)

At Baseline, the following procedures will be carried out:

1. Physical examination, including body weight and vital statistics.
2. Urine pregnancy test for all females of child-bearing potential.
3. Review concomitant medications.
4. Collection of a blood sample for qHBV DNA, qHBsAg, qAnti-HBs, HBeAg, anti-HBe and anti-HIV (anti-HIV is only for subjects at high risk of contracting HIV according to the discretion of the investigator).
5. Collection of a blood sample to be stored for exploratory analyses of HBV RNA, HBV core-related antigen (HBcrAg), qAnti-HBc, quantitative cccDNA, HBs fragments, HBsAg-anti-HBs immune complex, immunological studies and/or host DNA (to assess relationships with virologic response).
6. Collection of a blood sample for laboratory tests including hemoglobin, hematocrit, complete blood count (total and differential), platelet count, PT, INR, albumin, AST, ALT, GGT, CPK, alkaline phosphatase, bilirubin (total/direct), BUN, creatinine, sodium, potassium, chloride, and AFP.

7. Collection of blood samples for trough (just prior to dosing) plasma levels of NrtI and tizoxanide.
8. Collection of a urine sample for routine urinalysis (appearance, glucose, protein and blood).
9. Obtain a 12-lead electrocardiogram (ECG).
10. Instruct the subject regarding:
 - a. Administration of study medication.
 - b. Use of birth control. Female subjects of childbearing potential, if sexually active, will be instructed to continue an acceptable method of birth control for the duration of the study and for one month post-treatment. Acceptable methods of birth control include a double barrier method, oral birth control pills, an IUD, or medroxyprogesterone acetate administered intramuscularly.
 - c. Study visits. Subjects will be provided instructions for returning to the clinic for study visits.
 - d. Seeking emergency care or contacting the study physician or nurse. Subjects must be instructed to seek emergency medical care or contact the study physician or nurse if he/she develops any of the following symptoms during the study (treatment period or off-treatment follow-up period).
 - CALL 911 (United States) or LOCAL EMERGENCY SERVICES (outside the United States) OR HOSPITAL OR CONTACT STUDY PHYSICIAN IF YOU HAVE:
 - Trouble breathing including shortness of breath.
 - Severe pain in your chest, shoulder or belly.
 - CALL STUDY NURSE OR PHYSICIAN IF YOU EXPERIENCE:
 - Fever that does not go away or gets higher.
 - Feeling very weak or tired.
 - Unusual (not normal) muscle pain.
 - Trouble breathing.
 - Stomach pain or nausea and vomiting.
 - Feeling cold, especially in your arms and legs.
 - Feeling dizzy or light-headed.
 - Fast or irregular heartbeat.
 - Yellowing of eyes or sclera.
 - Brown or dark urine.
 - Confusion.
 - Tightness in your throat or chest, rash (especially hives) or itchiness.

- Loss of appetite for several days or longer.
- Bowel movements (stools) turn light in color.

11. Randomization (see [Section 8](#)).

At the Baseline visit, subjects will be randomly assigned to one of the following treatment groups:

Group 1: PLACEBO - Subjects will receive three placebo tablets twice daily with food in addition to continuing TDF, TAF or ETV therapy.

Group 2: 600 mg NTZ QD - Subjects will receive two NTZ 300 mg extended release tablets and one placebo tablet in the morning and three placebo tablets in the evening with food in addition to continuing TDF, TAF or ETV therapy.

Group 3: 600 mg NTZ BID - Subjects will receive two NTZ 300 mg extended release tablets and one placebo tablet twice daily with food in addition to continuing TDF, TAF or ETV therapy.

Group 4: 900 mg NTZ BID - Subjects will receive three NTZ 300 mg extended release tablets twice daily with food in addition to continuing TDF, TAF or ETV therapy.

Subjects will be given a 4-week supply of medication and instructions on administration of the study medication. The NTZ and placebo tablets (yellow) must be administered with food. TDF, TAF or ETV tablets should be administered daily at the same time each day. The first dose of study medication should be taken in the clinic under the observation of the investigator.

9.3. Evaluations During Treatment

Subjects will return to the clinic for evaluation at Day 3, and Weeks 1, 2, 4, 8, 12, 16, 20, 24 and every 12 weeks thereafter during treatment. Visit windows will be ± 1 day through Week 4 and ± 3 days thereafter. The following evaluations will be performed:

1. A brief physical examination including body weight and vital statistics
2. A urine pregnancy test for all females of child-bearing potential (except for Day 3)
3. Review concomitant medications
4. Collection of blood sample for qHBV DNA, qHBsAg, qAnti-HBs, HBeAg, anti-HBe and anti-HIV (anti-HIV is only for subjects at high risk of contracting HIV according to the discretion of the investigator)
5. Collection of blood sample to be stored for exploratory analyses of HBV RNA, HBcrAg, qAnti-HBc, quantitative cccDNA, HBs fragments, HBsAg-anti-HBs immune complex, immunological studies and/or host DNA (to assess relationships with virologic response)
6. Collection of blood sample for laboratory safety: hemoglobin, hematocrit, complete blood count, (total and differential), platelet count, PT, INR, AST, ALT, GGT, CPK, alkaline phosphatase, bilirubin total/direct, albumin, BUN, creatinine, sodium, potassium, chloride, and AFP (except for Day 3).

7. Collection of blood samples for trough (just prior to dosing) plasma levels of NrtI and tizoxanide.
8. Collection of a urine sample for routine urinalysis (appearance, glucose, protein and blood) (except for Day 3).
9. Obtain a 12-lead ECG (Week 12 and end of treatment visits only).
10. FibroScan® testing (at end of treatment only).
11. Ultrasonography for HCC screening (every 6 months).
12. Review of adverse events/side effects.
13. Review of compliance, collection of any unused medications from the previous visit, and dispense new supply of study medication.

9.4. Follow-up After End of Treatment with NTZ/Placebo

Subjects will return to the clinic for follow-up evaluation 4, 8 and 12 weeks after the end of treatment with the investigational medication (NTZ/placebo). In the event that a subject has sustained HBsAg loss with HBV DNA suppression at the Week 12 follow-up visit, that subject will also return for additional follow-up visits at 24 and 48 weeks after the end of treatment. The following evaluations will be performed during each follow-up visit:

1. Brief physical examination including body weight and vital statistics.
2. Review concomitant medications.
3. Collection of blood sample for qHBV DNA, qHBsAg, qAnti-HBs, HBeAg, anti-HBe and anti-HIV (anti-HIV is only for subjects at high risk of contracting HIV according to the discretion of the investigator).
4. Collection of blood sample to be stored for exploratory analyses of HBV RNA, HBcrAg, qAnti-HBc, quantitative cccDNA, HBs fragments, HBsAg-anti-HBs immune complex, immunological studies and/or host DNA (to assess relationships with virologic response).
5. Collection of blood sample for laboratory safety: hemoglobin, hematocrit, complete blood count, (total and differential), platelet count, PT, INR, AST, ALT, GGT, CPK, alkaline phosphatase, bilirubin total/direct, albumin, BUN, creatinine, sodium, potassium, chloride, and AFP.
6. Collection of urine sample for routine urinalysis (appearance, glucose, protein and blood).
7. FibroScan® testing (at end of follow-up only).
8. Ultrasonography for HCC screening (every 6 months).
9. Review of adverse events/side effects.

All adverse events must be followed up until they resolve or have stabilized (even beyond the follow-up visit dates provided above).

9.5. Unscheduled Visit

Subjects returning to the clinic for an unscheduled visit due to adverse events will be evaluated at the discretion of the Investigator as is medically warranted. Tests and/or procedures performed at this visit may include, but are not limited to the following:

1. Physical examination, including body weight and vital statistics.
2. Review of compliance with study medication.
3. Review concomitant medications.
4. Collection of blood sample for qHBV DNA, qHBsAg, qAnti-HBs, HBeAg, anti-HBe and anti-HIV (anti-HIV is only for subjects at high risk of contracting HIV according to the discretion of the investigator).
5. Collection of blood sample for laboratory safety: hemoglobin, hematocrit, complete blood count, (total and differential), platelet count, PT, INR, AST, ALT, GGT, CPK, alkaline phosphatase, bilirubin total/direct, albumin, BUN, creatinine, sodium, potassium, chloride, and AFP.
6. Collection of urine sample for routine urinalysis (appearance, glucose, protein and blood).
7. Review of adverse events/side effects.

9.6. Study Medication Discontinuation and Withdrawal Criteria

Treatment with the investigational medication (NTZ/placebo) will be discontinued for individual subjects for the following reasons:

1. Subject withdraws consent.
2. A subject must discontinue study medication for the following medical or administrative reasons [reasons for discontinuing must be recorded in the case report form (CRF)]:
 - Violation of eligibility criteria.
 - Material deviation from the treatment plan specified in the protocol.
 - Progression of the disease which in the opinion of the investigator precludes further participation.
 - Women who become pregnant.
3. An adverse event deemed sufficiently severe to require study discontinuation. These include:
 - Grade 2 or higher rash at least possibly related to study drug.
 - Grade 3 or 4 acute systemic allergic reaction.
 - Grade 2 serum creatinine considered at least possibly related to the study drug by the investigator, or Grade 3 or 4 proteinuria on urinalysis, confirmed by retesting.
 - Grade 2 vomiting that persists despite anti-emetics, or Grade 3 or higher vomiting.
 - Grade 3 or higher diarrhea at least possibly related to study drug.

- Treatment-emergent elevation of ALT greater than 2x baseline, in combination with either bilirubin greater than 2x the upper limit of normal (ULN) or INR greater than 1.5x ULN or serum albumin less than the lower limit of normal (LLN), confirmed by retesting.
- Any Grade 4 AE or confirmed abnormality (except for AST/ALT elevations) considered at least possibly related to the study drug.
- Clinical signs of hepatic decompensation.
- QTcF prolongation (QTcF greater than 500 msec, or increase from baseline greater than 60 msec) at any time point, confirmed by repeat ECG.

4. Subject is:

- HBsAg positive with no decline in qHBsAg from Baseline at Week 12.
- HBsAg positive with less than a $0.5 \log_{10}$ decline in qHBsAg from Baseline at Week 24.
- HBsAg positive with less than a $1 \log_{10}$ decline in qHBsAg from Baseline at Week 48.
- HBsAg positive with less than a $2 \log_{10}$ decline in qHBsAg from Baseline at Week 72.
- HBsAg positive at Week 96.

5. HBsAg loss with HBV DNA suppression maintained on treatment for 24 weeks (consolidating therapy).

IMPORTANT: TDF, TAF or ETV therapy will only be discontinued after a subject experiences sustained HBsAg loss with HBV DNA suppression for 24 weeks on treatment (consolidating therapy). Otherwise, subjects will continue TDF, TAF or ETV therapy after discontinuing the investigational medication (NTZ/placebo).

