13.2. Clinical Adverse Events

At the time of each return visit, the subject will be questioned regarding the occurrence and nature of any adverse events. All events must be recorded in the subjects' medical records and in the EDC system. Any subject affected will be examined by the Investigator as deemed necessary to ascertain the course of the event and any residual effects.

All moderate and severe adverse events will be reviewed by the Principal Investigator who will determine using his/her best clinical judgment whether they warrant the subject to be discontinued from the study. The Sponsor will be notified immediately if a subject is discontinued from the study. For all adverse events that require the subject to be discontinued from the study, relevant clinical assessments and laboratory tests will be repeated as clinically indicated until final resolution or stabilization of the event(s).

All subjects will be instructed to contact the Investigator, Investigator's assistants, or clinical personnel should the subject have any serious adverse experiences. Serious adverse events,

including death regardless of the cause, must be reported to the Sponsor immediately (within 24 hours of the initial report).

A serious event requiring immediate notification by telephone is an event that:

- results in death
- is life threatening
- requires inpatient hospitalization or prolongation of an existing hospitalization
- is a persistent or significant disability/incapacity
- is a congenital anomaly/birth defect
- an important medical event that may not result in death, be life-threatening, or require hospitalization but, based upon appropriate medical judgment, may jeopardize the subject and may require medical or surgical intervention to prevent one of the outcomes listed above.

An overdose is defined as any intentional or unintentional consumption of the drug by any route that exceeds the highest dose stated in the Investigator's Brochure, approved product labeling (for TDF, TAF or ETV) or in an investigational protocol, whichever dose is larger. Overdoses without an associated adverse event should be recorded, but not reported as an adverse event.

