13.4. Medication Modification/Withdrawal Due to Adverse Event

If a severe adverse reaction or laboratory abnormality develops during combination therapy, the dose should be modified or discontinued, at the discretion of the Investigator and in accordance with the approved product labeling for TDF, TAF or ETV, until the adverse reaction abates. If intolerance persists after the dose has been adjusted, the study medication should be discontinued.

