Creatinine, High *Report only one	1.1 to 1.3 x ULN	> 1.3 to 1.8 x ULN OR Increase to 1.3 to < 1.5 x participant's baseline	> 1.8 to < 3.5 x ULN OR Increase to 1.5 to < 2.0 x participant's baseline	≥ 3.5 x ULN OR Increase of ≥ 2.0 x participant's baseline

PARAMETER	GRADE 1 MILD	GRADE 2 MODERATE	GRADE 3 SEVERE	GRADE 4 POTENTIALLY LIFE-THREATENING
Creatinine Clearance or eGFR, Low *Report only one (i.e., Cockcroft-Gault in mL/min or Schwartz, MDRD, CKD-Epi in mL/min/1.73 m²)	NA	< 90 to 60 mL/min or mL/min/1.73 m ² OR 10 to < 30% decrease from participant's baseline	< 60 to 30 mL/min or mL/min/1.73 m ² OR 30 to < 50% decrease from participant's baseline	< 30 mL/min or mL/min/1.73 m ² OR ≥ 50% decrease from participant's baseline or dialysis needed
Glucose (mg/dL; mmol/L) Fasting, High	110 to 125 6.11 to < 6.95	> 125 to 250 6.95 to < 13.89	> 250 to 500 13.89 to < 27.75	≥ 500 ≥ 27.75
Glucose (mg/dL; mmol/L) Nonfasting, High	116 to 160 6.44 to < 8.89	> 160 to 250 8.89 to < 13.89	> 250 to 500 13.89 to < 27.75	≥ 500 ≥ 27.75
Glucose, Low (mg/dL; mmol/L)	55 to 64 3.05 to < 3.55	40 to < 55 2.22 to < 3.05	30 to < 40 1.67 to < 2.22	< 30 < 1.67
Lactate, High	ULN to < 2.0 x ULN without acidosis	≥ 2.0 x ULN without acidosis	Increased lactate with pH < 7.3 without life-threatening consequences	Increased lactate with pH < 7.3 with life-threatening consequences
Lipase, High	1.1 to < 1.5 x ULN	1.5 to < 3.0 x ULN	3.0 to < 5.0 x ULN	≥ 5.0 x ULN
Lipids Disorders: Cholesterol, Fasting, / High (mg dL; mmol/L)	200 to < 240 5.18 to < 6.19	240 to < 300 6.19 to < 7.77	≥ 300 ≥ 7.77	NA
Lipids Disorders: LDL, Fasting, High (mg dL; mmol/L)	130 to < 160 3.37 to < 4.12	160 to < 190 4.12 to < 4.90	≥ 190 ≥ 4.90	NA
Lipids Disorders: Triglycerides, Fasting, High (mg dL; mmol/L)	150 to 300 1.71 to 3.42	> 300 to 500 > 3.42 to 5.7	> 500 to < 1,000 > 5.7 to 11.4	> 1,000 ≥ 11.4
Magnesium, Low (mEq/L; mmol/L) (To convert a magnesium value from mg/dL to mmol/L, laboratories should multiply by 0.4114)	1.2 to < 1.4 0.60 to < 0.70	0.9 to < 1.2 0.45 to < 0.60	0.6 to < 0.9 0.30 to < 0.45	< 0.6 ≤ 0.30
Phosphate, Low (mg/dL; mmol/L)	2.0 to < LLN 0.65 to < LLN	1.4 to < 2.0 0.45 to < 0.65	1.0 to < 1.4 0.32 to < 0.45	< 1.0 ≤ 0.32

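### The creatinine stopping rule in Section 9.6 names Grade 2 without 'or higher', so a related Grade 3 rise has no listed mandatory stop

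*Combined protocol and SAP*

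**What the plan says.** Item 3 of Section 9.6 introduces, with the word 'include', the adverse events severe enough to require stopping. Three of its entries matter here:

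- Creatinine: "Grade 2 serum creatinine considered at least possibly related to the study drug by the investigator". The same bullet goes on to Grade 3 or 4 proteinuria and ends with confirmation by retesting.
- Rash, for comparison: "Grade 2 or higher rash at least possibly related to study drug". The vomiting and diarrhea bullets also carry 'or higher', and the allergic-reaction bullet names both Grade 3 and Grade 4.
- The catch-all: "Any Grade 4 AE or confirmed abnormality (except for AST/ALT elevations) considered at least possibly related to the study drug".

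Two other sections apply to events that the list does not name. Section 13.2 states: "All moderate and severe adverse events will be reviewed by the Principal Investigator who will determine using his/her best clinical judgment", the question being whether the subject should be discontinued. Section 13.4 says that for a severe reaction or laboratory abnormality "the dose should be modified or discontinued, at the discretion of the Investigator".

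Table 5 (Appendix III, Section 23.3) defines Grade 3 creatinine as "> 1.8 to < 3.5 x ULN", or by the alternative criterion "Increase to 1.5 to < 2.0 x" the participant's baseline.

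**The concern.** A stopping rule should not become weaker as the finding becomes worse. As written, the milder grade obliges the site to stop and the next grade up does not. The words 'Grade 3 or 4' in the creatinine bullet belong to proteinuria, so they do not fill the gap. Creatinine is the only grade-based bullet that names a single grade with nothing above it, which gives a literal reader some reason to think the difference is deliberate.

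What is at stake is consistent protection of individual subjects. Given the same related Grade 3 value, one investigator would stop study drug because Grade 2 reads as a minimum. Another could rely on Section 13.4 and adjust the dose instead. No other rule protects the individual: the study-level rule in Section 14 needs more than 20% of subjects with related Grade 3 or 4 events, and Section 16 says there is no independent data monitoring committee.

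**Working it through.** The plan gives no figure to reproduce on this point. The check sets each Table 5 creatinine grade against the stop list, for a rise judged at least possibly related.

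| Grade | x ULN | x baseline | Listed stop in Section 9.6? |
|---|---|---|---|
| 1 | 1.1 to 1.3 | none given | No |
| 2 | >1.3 to 1.8 | 1.3 to <1.5 | Yes, creatinine bullet |
| 3 | >1.8 to <3.5 | 1.5 to <2.0 | **No**; Sections 13.2 and 13.4 apply |
| 4 | ≥3.5 | ≥2.0 | Yes, Grade 4 catch-all |

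With 'Grade 2 or higher', Grades 2, 3 and 4 would all be listed stops.

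**Width of the gap on the baseline scale.** Grade 3: 2.0 − 1.5 = 0.5 x baseline. Grade 2: 1.5 − 1.3 = 0.2 x baseline. These widths describe the rule and say nothing about how often values fall in each band.

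**Ways to reach Grade 3 with no confirmed Grade 2 reading.**

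1. *Between visits.* On the baseline scale, a subject just under 1.3 x baseline needs a further rise of 1.5/1.3 = 1.154, about 15%. A subject still at baseline needs 50%. Section 9.3 schedules visits after Week 24 "every 12 weeks thereafter during treatment". Up to Week 24 the scheduled safety bloods are at most 4 weeks apart.
2. *By the higher-grade rule.* The general instructions in Appendix III say that an event which could take either of two grades is given the higher. A creatinine of 1.5 x ULN and 1.6 x baseline is Grade 2 by ULN and Grade 3 by baseline. It is graded 3 and so falls outside the literal criterion.
3. *At the retest.* If the first value is Grade 2 and the confirmatory value has worsened to Grade 3, a literal reader has no confirmed Grade 2.

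**What such a value may look like (assumption).** Suppose baseline creatinine is 0.6 to 0.9 x ULN; the documents do not give this range. Grade 3 by baseline then starts at 1.5 x 0.6 = 0.90 to 1.5 x 0.9 = 1.35 x ULN. A value near the upper limit of normal may not look alarming, so discretion could plausibly be used to continue.

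A subject already stopped at a confirmed Grade 2 is not affected.

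**The case against.** The strongest reply is that nobody would read the bullet this way. The list is open, and if a related Grade 2 rise is severe enough to require a stop, a related Grade 3 rise must be too. That is very likely what was intended, and it is why this is best seen as a drafting slip. It does not make the stop a stated requirement.

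Other points have some force:

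- The Grade 2 stop is not automatic either, since it depends on the investigator's view of relatedness and on a retest. True, but judging relatedness is different from judging whether to stop. Once both conditions are met, Grade 2 leaves no choice.
- Section 13.4 refers only to the labeling of TDF, TAF or ETV, and the protocol has no dose-reduction scheme for the blinded tablets. So modifying the dose of study drug would be awkward. A temporary hold remains possible, however, and the section does foresee adjusting the dose before study medication is discontinued.
- The 12-week interval applies only to subjects still on drug after Week 24, which requires at least a 0.5 log10 decline in qHBsAg. Before then a gradual rise would probably show a Grade 2 value first. This limits the first route above but not the other two.
- Creatinine clearance below 65 ml/minute is excluded, so few subjects are likely to be affected. Accepted.

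These points reduce the expected impact. They do not remove the reversed ordering of Grades 2 and 3.

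**Conclusion.** The concern holds. As written, a related Grade 3 creatinine has no listed mandatory stop, while the grades on either side of it do. Grade 3 is not without provision, because the open list, Principal Investigator review and Section 13.4 all allow a stop; none requires one.

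The conclusion rests on the text of Section 9.6 and Table 5 and on no numerical assumption. The number of subjects exposed to the gap cannot be calculated, since the documents give no expected rate of creatinine rise; with 48 subjects it is probably small. Sample size, power, the primary analysis and blinding are unaffected. The correction is worth making because the bullet is an operative safety threshold.

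**What to change.** In Section 9.6, item 3, insert 'or higher' after 'Grade 2' in the creatinine bullet, so that it opens with *Grade 2 or higher serum creatinine* and matches the form of the rash bullet. Leave the relatedness and retest conditions as they are. Nothing needs to be added for Grade 1 creatinine or for proteinuria.

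The cost is two words in a protocol amendment. Visits, data collected, analysis and blinding do not change. If the sponsor already means Grade 2 as a minimum, the edit only removes the ambiguity.
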